3. STUDY DESIGN

The present research study design will utilize an individually randomized group treatment, open-label, waitlist-controlled clinical trial to test the efficacy and safety of our innovative mindfulness meditation intervention (Training for Awareness Resilience and Action [TARA]) on the primary outcome (Putamen structural node strength) and secondary outcome (emotional problems measured with the Strengths and Difficulties Questionnaire [SDQ]) in healthy adolescents between the ages of 14 to 18 years old.

The specific unit of assignment and unit of observation are the individual study participants.

[figure not shown]
Primary outcome: Putamen structural node strength

Secondary outcome: Emotional problems measured with the Strengths and Difficulties Questionnaire (SDQ)

The study population are 100 healthy adolescents that are 14-18 years old, who are randomly assigned to the intervention or waitlist control group (50 assigned to intervention, 50 assigned to waitlist control who will later receive the intervention).

The entire study will take place at the University of California, San Francisco (UCSF). More specifically, all of the MRI scans will take place at the UCSF Mission Bay campus. All of the TARA group interventions and subject interviews will take place remotely over Zoom.

The approximate duration of subject enrollment period for the entire trial will be 21 months (please see below, R61 Phase Timeline). We plan to run 5 intervention groups and 5 waitlist control groups. The intervention duration is 1.5 hours per week for 12 weeks, and MRI scanning and clinical assessments will be performed within 2 weeks (maximum 4 weeks) before and after the 12-week intervention. Thus, each individual participant who is randomly assigned to the intervention will be followed for a total duration of up to 20 weeks (12 weeks of intervention plus up to 4 weeks before the start of the intervention plus up to 4 weeks after the end of the intervention). The individual participants who are randomly assigned to the waitlist control will be similarly followed for approximately 20 weeks.

Intervention: 12-week group meditation training, Training for Awareness, Resilience, and Action (TARA).

We will use computer-generated randomization with variable blocks sizes of 4, 6 and 8. Individuals will be randomized with no stratification, matching or constraints except the permuted blocks. We will permute 8 blocks of size 8, 2 blocks of size 6, and 4 blocks of size 4. The treatment assignments will be 1:1 within each block and assignments within a block will be permuted. The only masking will be in the administration of questionnaires and in the interpretation of putamen node strength.

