Adolescents and their parents/guardians will be screened using a semi-scripted telephone screening procedure designed to elicit inclusion/exclusion information and provide additional information about the study to the caller. The parent and adolescent will provide **verbal consent** to answer some questions over the telephone to pre-screen the adolescent regarding eligibility (e.g. age 14-18 years, healthy, English-speaking) as well as **verbal consent** to study participation, and availability

for study assessments and classes. The study procedures, including what is involved in participating in the training, as well as the MRI visits will be described to potential participants and their parents. The goal is to ensure they understand the commitment involved in study participation. Those who do not meet eligibility criteria will be told that they are not eligible to participate. **First visit**: Those who meet inclusion criteria and give **verbal consent** will schedule the first visit which will include the questionnaire-based assessments (First visit Part A) and baseline MRI scan (First visit Part B). The **consent form** will be mailed or emailed for review prior to the visit. At the First visit Part A, which can be conducted over Zoom, the researcher will first review the **consent form** with the adolescent and the parent/guardian, and they will **both sign the form** using DocuSign. Electronic copies of all consent forms will be provided to the participant and to the parent or legal guardian, as well as the Experimental Subjects Bill of Rights. No adolescents will be contacted or screened by the study team before parental verbal consent is obtained. The exception is the 18-year-old participants who do not need parental consent.

We will use computer-generated randomization with random blocks sizes ranging from 4 to 8 in order to assign a participant to either the TARA intervention group or the waitlist control group.

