9. STATISTICAL CONSIDERATIONS

9.1 General Design Issues

This is a randomized open-label waiting list controlled study of TARA training in 100 boys and girls aged 14-18 years. They will be individually randomized to 12 weeks of group TARA training sessions (50 to TARA training and 50 to waitlist control). The randomization is open label because there was concern that it was not possible to develop a sham training which would motivate participation and yet have no effects on the desired outcomes.

This study is designed to demonstrate that the TARA training will increase putamen connectivity (primary outcome) and decrease emotional problems on the SDQ questionnaire (secondary outcome).

Primary Hypothesis: Putamen structural node strength (primary outcome) will increase in the training group compared to controls.

Secondary Hypothesis: There will be a significant decrease in emotional problems measured with the Strengths and Difficulties Questionnaire (SDQ) (secondary outcome) in the training group compared to controls.

In our recent published study (Yuan et al., 2019), we demonstrated that diffusion MRI connectome methods can provide reliable and precise network measures, including the node strength, in adolescents.

The SDQ was selected because it is widely used in adolescents to measure internalizing problems and has good psychometric properties (Goodman, 2001).

For more details see section 10.3.3 Metrics.

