9.2. Sample Size and Randomization

The study is powered for medium-large effect size of the meditation training on the putamen node strength. With type I error of 0.05, type II error of 0.2 (power of 80%), two-sided effect size of a Cohen's D of 0.6, the required sample size is N=45 subjects who will be studied before and after the TARA training. Given the length of the study (three months), the required commitment to participation in the training, and based on our experience, we assume an attrition rate of 10%; therefore, the target sample size is 50 subjects per group. Our primary analysis will be a general linear model of putamen node strength at week 12 with terms for baseline node strength, treatment assignment and participant sex. The primary analysis will be intent to treat and will include all randomized participants regardless of treatment receipt or protocol violations.

The only clustering in the trial will be the group delivery of the TARA intervention. We anticipate 4 TARA classes of 10-15 participants. We expect the intraclass correlation to be negligible for the following reasons: a) the TARA instructors are trained in standard procedures, b) we expect formidable individual level variation. We therefore did not include cluster assignment in the sample size calculation. We are going to test this assumption in a sensitivity analysis which extended the primary analysis by inclusion of treatment by TARA class interaction.

To standardize TARA delivery, we have included facilitator training and created a very detailed TARA manual (please see Appendix).

Treatment Assignment Procedures

We will use computer-generated randomization with variable blocks sizes of 4, 6 and 8. Individuals will be randomized with no stratification or restricted except the permuted blocks. We will permute 8 blocks of size 8, 2 blocks of size 6, and 4 blocks of size 4. The treatment assignments will be 1:1 within each block and assignments within a block will be permuted. The only masking will be in the administration of questionnaires and in the interpretation of putamen node strength.

The rationale for the use of randomization is to minimize potential biases.

The study is open label to participants, and thus there is no need for unblinding or unblinding procedures.

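### The listed randomization blocks supply 92 assignments (46 per arm), not the planned 100 (50 per arm)

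*Combined protocol and SAP*

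**What the plan says.** Section 3 (Study Design) describes computer-generated permuted blocks of sizes 4, 6 and 8 and then gives the number of each: "We will permute 8 blocks of size 8, 2 blocks of size 6, and 4 blocks of size 4". Section 9.2, under Treatment Assignment Procedures, repeats these counts.

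Within blocks, "The treatment assignments will be 1:1 within each block and assignments within a block will be permuted". There is a single list: "Individuals will be randomized with no stratification, matching or constraints except the permuted blocks".

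The number to be randomized is 100 throughout. Section 3 has "50 assigned to intervention, 50 assigned to waitlist control who will later receive the intervention", and Section 9.1 has "50 to TARA training and 50 to waitlist control". The Précis states the same split, and the go/no-go criterion in Section 1.1 refers to 100 adolescents.

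Section 9.2 derives that number from "two-sided effect size of a Cohen's D of 0.6, the required sample size is N=45 subjects" and then "we assume an attrition rate of 10%; therefore, the target sample size is 50 subjects per group".

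Section 4.3 describes the blocks more loosely and without counts: "We will use computer-generated randomization with random blocks sizes ranging from 4 to 8".

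**The concern.** Once a protocol states how many blocks of each size will be used, it has fixed the length of the allocation list. That length should equal the number to be randomized, or exceed it with a stated reserve. Here it falls short of the planned number, and the same shortfall appears in both sections that give the counts.

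Two things are at stake:

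- **Size of the trial.** If the list defines the end of enrolment, the trial stops at 92 and most of the allowance for attrition is gone.
- **Allocation of the last participants.** If enrolment continues to 100, participants 93 to 100 are assigned by a step the plan does not describe. Participants and instructors know the assignments (Section 5.2 and Table 1), so a pre-generated, documented list is one of the main protections against selection at entry. An unplanned addition at the end weakens that documentation.

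**Working it through.** **Inputs.** Block counts and sizes: Sections 3 and 9.2. Ratio 1:1 and no stratification: Section 3. Planned total 100, 50 per arm: Sections 3 and 9.1. Two-sided alpha 0.05, power 80%, d = 0.6, required N = 45, attrition 10%, target 50 per group: Section 9.2.

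**Step 1: is the target of 100 sound?** For two independent groups, the normal approximation is n per arm = 2(1.96 + 0.84)² / d² = 2 × 7.85 / 0.36 = 43.6, so 44. The two-sample t-test gives 44.6, so 45, which is the plan's figure. A one-sample (before-after) calculation would need only 23.8, so the stated 45 is a per-arm figure for a two-group comparison. Inflating for attrition, 45 / 0.90 = 50 per arm, or 100 in total. The plan's sample size reproduces.

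**Step 2: length of the list.** Sum of (number of blocks × block size):

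| Block size | Number | Assignments |
|---|---|---|
| 8 | 8 | 64 |
| 6 | 2 | 12 |
| 4 | 4 | 16 |
| **Total** | **14** | **92** |

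At 1:1 this is 92 / 2 = 46 per arm. The shortfall is 100 − 92 = 8, or 4 per arm (8% of the planned total).

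**Step 3: could the counts have been transposed?** The counts 8, 2 and 4 can be attached to the three sizes in six ways:

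| Blocks of 8 | Blocks of 6 | Blocks of 4 | Total |
|---|---|---|---|
| 8 | 2 | 4 | 92 |
| 8 | 4 | 2 | 96 |
| 4 | 8 | 2 | 88 |
| 2 | 8 | 4 | 80 |
| 4 | 2 | 8 | 76 |
| 2 | 4 | 8 | 72 |

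None reaches 100, so a simple swap does not explain the gap. Because the counts are the same in two separate sections, a fault in reading one passage does not explain it either.

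**Step 4: consequence if enrolment stops at 92.** After the plan's 10% attrition, 46 × 0.90 = 41.4 per arm remain. Two-sample power at d = 0.6, two-sided 0.05 (t-test noncentrality d√(n/2), with 2n − 2 degrees of freedom):

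| Evaluable per arm | t-test | Normal approximation |
|---|---|---|
| 45 (planned) | 0.804 | 0.812 |
| 41.4 | 0.770 | 0.779 |
| 41 | 0.765 | 0.775 |

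The loss is 3 to 4 percentage points. The room for attrition before falling below 45 drops from 5 per arm (50 − 45) to 1 per arm (46 − 45).

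**Step 5: smallest corrections.** One more block of 8: 72 + 12 + 16 = 100. Two more blocks of 4: 64 + 12 + 24 = 100.

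**The case against.** The sum cannot be disputed; the objection is to its weight.

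- **No bias in the comparison.** Every listed block is balanced, the arms stay equal and the estimand is unchanged. Even at 92, the 46 randomized per arm exceed the 45 evaluable that Section 9.2 requires; the deficit appears only after attrition. This stands.
- **The power loss is conditional and may be pessimistic.** No section says enrolment would stop at 92. The primary model adjusts for baseline node strength and sex, whereas the 77% is unadjusted. The documents give no baseline to follow-up correlation. If d = 0.6 is taken on the follow-up standard deviation, power at 41.4 per arm would be about 0.81, 0.88 or 0.97 for assumed correlations of 0.3, 0.5 or 0.7. This also stands, but the plan's 45 was itself derived without adjustment, so 77% is the like-for-like figure.
- **Another block can simply be added.** Section 4.3 allows random sizes from 4 to 8 without a cap, and a further concealed block is ordinary practice and need not be predictable. This is a fair description of the remedy. It does not remove the contradiction, because an added block lies outside the set that Sections 3 and 9.2 specify and the plan makes no provision for one.
- **The actual list has not been seen.** It may hold 100 assignments. If so, the protocol misdescribes it and still needs correcting.

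**Conclusion.** The concern holds. The block set in Sections 3 and 9.2 yields 92 assignments, 46 per arm, against a planned 100, 50 per arm. The arithmetic is exact and needs no assumption beyond the stated 1:1 ratio and a single unstratified list. The sample-size derivation is internally consistent, so the block counts are what is wrong.

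The statistical effect is modest. Power falls from about 80% to about 77%, assuming that enrolment stops at 92, that attrition is 10%, and that the comparison is the unadjusted two-sample one behind the plan's 45. If enrolment continues to 100, the cost is instead that 8 participants are allocated by an unspecified step. The reason to insist on correction is not the size of the power loss but that a figure in the allocation specification of a randomized trial is wrong as written, and that putting it right costs almost nothing.

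**What to change.** 1. Change the block counts in Sections 3 and 9.2 so that they sum to 100. Nine blocks of 8, two of 6 and four of 4 is one way; eight of 8, two of 6 and six of 4 is another.
2. Align Section 4.3, which gives a range of sizes only, with the same scheme.
3. Check the list actually held and confirm that it has 50 assignments per arm.
4. If the list is short and no one has been randomized, regenerate or extend it. If anyone has been randomized, extend it only: generate the missing block or blocks by the same computer method, by someone not involved in enrolment, before the existing blocks are used up, and record the date and reason.

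The cost is one number in two sections, a consistent sentence in a third, and a check of the list. No endpoint, analysis or participant procedure changes. The one thing to avoid is replacing a list that is already in use.

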11. PARTICIPANT RIGHTS AND CONFIDENTIALITY	
12. COMMITTEES	39
13. PUBLICATION OF RESEARCH FINDINGS	39
14. REFERENCES	39
15. SUPPLEMENTS/APPENDICES	41
 Phone Pre-Screening of Inclusion/Exclusion Criteria Informed Consent Form for 14-17-year-old participants Informed Consent Form for 18-year-old participants Medical History Form Inclusion/Exclusion Criteria Form Enrollment/Randomization Form MRI Screening Form SDQ questionnaire Demographics questionnaire Baseline Checklist Form CORS CSRS On Study Visit Checklist Adverse Events Form 	
Serious Adverse Events Form	

• Study Completion Form

• TARA manual

• Protocol Deviation Tracking Log

STUDY TEAM ROSTER

[name],
Department of Radiology & Biomedical Imaging
University of California, San Francisco
[name]
[name]
[contact]

[contact] [contact]

[name], PhD, Department of Psychiatry, University of California, San Francisco [name] Langley Porter Psychiatric Institute [name] [contact]

[contact] [name]. [contact]

PARTICIPATING STUDY SITES

It is a single site study: please see the names and addresses above.

PRÉCIS

Study Title

Neural mechanisms of meditation training in healthy and depressed adolescents: An MRI connectome study

Objectives

The **primary objective** will be to study changes in putamen structural connectivity in healthy teens with meditation training. **Hypothesis**: Putamen structural node strength will increase in the training group compared to controls.

R61 Go/No-Go Criteria. Detect an effect size (a threshold of Cohen's d > 0.20) in changes of the primary mechanistic outcome (**Putamen structural node strength**) by the described meditation training in 100 healthy adolescents that are 14-18 years old and retain at least 80% of randomized participants for primary outcome measurement at the end of the study regardless of adherence to the intervention.

[figure not shown]
The **secondary objective** will be to study changes in emotional problems in healthy teens with meditation training. **Hypothesis**: There will be a significant decrease in emotional problems measured with the Strengths and Difficulties Questionnaire (SDQ) in the training group compared to controls.

Design and Outcomes

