6.2.3 Blinding

There will be one unblinded research assistant (RA) who will be responsible for: (1) scheduling and helping set-up the delivery of the TARA intervention, and (2) providing unblinded case-by-case reports to the study Independent Monitors (IM); this RA will have no access to data and no involvement in data monitoring and analyses.

Since the Study subjects and TARA Instructors/Practitioners can not be blinded to the Intervention group assignment (please see below, Table 1 Blinding Table), there will not be an individual authorized to break the blind, circumstances for breaking the blind, or procedures for breaking the blind. Which stake holders will be blinded, what the stake holders will be blinded to, and the procedures for retaining the blind for the different stake holders for the intervention group assignment, primary mechanistic outcome measure, and clinical/functional outcome measure are described below in Table 1 (please see below, Table 1. Blinding Table).

Table 1. BLINDING TABLE

Stake holder	Intervention group assignment	Primary Mechanistic Outcome Measure	Clinical/ Functional Outcome Measure
Study subjects/Patients	Not blinded	Blinded	Blinded
casjooton anome	The study subjects/patients will know which intervention group they have been assigned to. Thus, by necessity, they will be only unblinded to the intervention group assignment.	The study subjects/patients will be blinded to the Primary Mechanistic Outcome Measure for the entire duration of the project.	The study subjects/patients will be blinded to the Clinical/Functional Outcome Measure for the entire duration of the project.
Instructors/ Practitioners	Not blinded	Blinded	Blinded
	The TARA Instructors/Practitioners must— by necessity—be only unblinded to the intervention group assignment in order to deliver the	All of the TARA Instructors/ Practitioners will be blinded to the Primary Mechanistic Outcome	All of the TARA Instructors/Practitioners will be blinded to the Clinical/Functional Outcome

	TARA intervention to the participants.	Measure for the entire duration of the study.	Measure for the entire duration of the study.

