10. DATA COLLECTION AND QUALITY ASSURANCE

10.1 Data Collection Forms

Information for each participant will be collected using the following forms and procedures:

- o Informed Consent Form (will be obtained and signed by RA via DocuSign)
- Medical History Form (source document, will be collected and signed by RA via DocuSign)
- o Inclusion/Exclusion criteria form (source document, will be filled out and signed by RA via DocuSign)
- Enrollment/Randomization form (source document, will be filled out and signed by RA via DocuSign)
- o MRI screening form (will be signed by the MRI technician. Not a source document.)
- o MRI brain scan (will be performed using a 3T MRI scanner)
- o Demographics assessment (will be performed electronically in Qualtrics)
- SDQ assessment (will be performed electronically in Qualtrics)
- Baseline Visit Checklist (source document, will be filled out and signed by RA via DocuSign)
- Child Session Rating Scale (CSRS) (source document, will be collected and signed by RA)
- Child Outcome Rating Scale (CORS) including the question: "Has there been any significant unfavorable change in your mental or physical health since last class?" (will be collected by RA. Not a source document.)
- o Adverse Events (source document, if the answer is Yes to the question above in CORS, this form will be filled out and signed by RA via DocuSign)
- Serious Adverse Events (source document, if answered Yes to the SAE question in the Adverse Event form, this form will be filled out by RA, signed by PI via DocuSign)
- o On Study Visit Checklist Form (source document, will be filled out and signed by RA via DocuSign)
- Study Completion form (source document, will be filled out by RA, signed by PI via DocuSign).

All source documents will be signed and stored electronically in DocuSign. Any data, forms, reports, video recordings, and other records that leave the site will be identified only by a participant identification number (Participant ID, PID) to maintain confidentiality. All computer entry and networking programs will be done

using PIDs only. Information will not be released without written permission of the participant, except as necessary for monitoring by the UCSF IRB, the NCCIH, and the OHRP.

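### The protocol prints the block make-up of its single allocation list and does not say which research assistant sees assignments; upcoming assignments would be partly guessable to anyone who sees past ones

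*Combined protocol and SAP*

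**What the plan says.** - **The list.** Section 3 (Study Design) states "We will permute 8 blocks of size 8, 2 blocks of size 6, and 4 blocks of size 4", and Section 9.2 repeats the sentence. Section 4.3 gives only the range: "random blocks sizes ranging from 4 to 8". Within blocks, "The treatment assignments will be 1:1 within each block and assignments within a block will be permuted". There is one list: "Individuals will be randomized with no stratification, matching or constraints except the permuted blocks".
- **The setting.** The front matter (Participating Study Sites) says "It is a single site study". Section 9.2 describes the trial as open label to participants. The planned allocation is "50 assigned to intervention, 50 assigned to waitlist control who will later receive the intervention" (Section 3).
- **Who handles the forms.** Section 10.1 lists "Enrollment/Randomization form (source document, will be filled out and signed by RA via DocuSign". The inclusion/exclusion form is likewise signed by an RA, and neither entry says which RA.
- **Who is unblinded.** Section 6.2.3 says "There will be one unblinded research assistant (RA) who will be responsible for" scheduling and setting up the TARA classes and supplying unblinded reports to the Independent Monitors. It also bars this RA from the data. Obtaining, releasing or recording assignments is not on the list.
- **Timing.** Section 6.2.2 puts the end of screening, baseline and randomization on the same day. Section 9.5.1 implies that baseline comes first, but no section makes release of an assignment conditional on it.
- **Safeguards.** Sections 5.2 and 6.2.3 blind the investigators, outcome assessors and analysts until database lock, and tell participants not to disclose their group to staff.

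The protocol text does not say who generates or holds the list, how an assignment is released, or which staff are kept from it.

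**The concern.** Blocks of varying size protect allocation when the people who enrol participants know neither the sizes nor the past assignments. Here the sizes and counts stand in the working protocol, and the text leaves open whether an RA who screens and enrols also records the arm.

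Sections 6.2.3 and 10.1 do not fit together as written. Either the unblinded RA completes the randomization form, and 6.2.3 omits that duty, or another RA does. In the second case, if the form shows the arm, a second RA is unblinded.

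A recruiter who can partly foresee the next arm may, without intending it, time or encourage the enrolment of keener volunteers. Some eligibility decisions involve judgement, for example on substance use (Section 4.2). The outcomes most exposed are the SDQ, a questionnaire given to participants who know their arm, together with attendance and retention by arm. Retention of at least 80% is also one of the go/no-go criteria in Section 1.1.

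**Working it through.** **Inputs.** From Sections 3 and 9.2: 8 blocks of 8, 2 of 6 and 4 of 4, allocated 1:1 within each block. Two assumptions are not in the documents: the guesser sees every past assignment, and the 14 blocks run in random order.

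**1. Size of the printed list.** 8×8 + 2×6 + 4×4 = 64 + 12 + 16 = 92 places, or 46 per arm. The plan is 100 (50 per arm), so the list is 8 places short. One more block of 8, or two more of 4, would give 100.

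**2. Average guessing rate.** Every completed block is balanced, so the running imbalance between arms equals the imbalance inside the current block. The best guess is always the arm that is behind, and it needs no knowledge of block sizes. For a block of size 2m, the expected number of correct guesses is m + 4^m / (2·C(2m, m)) − 1/2:

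- size 8 (m = 4): 4 + 256/140 − 0.5 = 5.329
- size 6 (m = 3): 3 + 64/40 − 0.5 = 4.100
- size 4 (m = 2): 2 + 16/12 − 0.5 = 2.833

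Total: 8×5.329 + 2×4.100 + 4×2.833 = 62.16 of 92, or 67.6%. In 1,500 simulated lists, an exact Bayesian guesser given the full make-up, one given only the sizes, and one given no sizes all scored 62.1 of 92 (67.5%).

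**3. Assignments known with certainty** (same simulation, except the last two rows):

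| Guesser's knowledge | Certain, of 92 | Correct on average |
|---|---|---|
| Past assignments and full make-up | about 5.1 (5.5%) | 67.5% |
| Past assignments and sizes 4/6/8 only, taken as equally likely | about 3.6 (3.9%) | 67.5% |
| Past assignments, no sizes | 0 | 67.5% |
| Past assignments and block order | 21.1 (23%) | 67.6% |
| No past assignments | 0 | 50% |

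The simulation standard error of the 5.1 and the 3.6 is about 0.08. The block-order row follows from the expected run of forced places at the end of a block, 2m/(m + 1): 8×1.6 + 2×1.5 + 4×1.333 = 21.1. It is an upper scenario, because the protocol does not print the order.

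**4. What drives the result.** Seeing past assignments moves the guess rate from 50% to about 67.5%. Printing the counts moves it by nothing, and adds about 1.5 certain assignments compared with knowing the sizes alone.

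**The case against.** A reader might infer that enrolling staff can predict upcoming assignments, and that printing the make-up removes the protection of varying blocks. The documents do not support either statement. The first needs one RA to sign every randomization form, the form to show the arm, and the same RA to recruit. Section 10.1 says only RA, other sections show there are several RAs, and the form is in an appendix that is not reproduced. The second fails on the figures above.

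The plan also has real safeguards: blinded investigators and assessors, an instruction to participants not to disclose their group, a yes/no eligibility form (Section 6.2.1), a substance-use screener (Section 4.2), and a primary MRI outcome adjusted for baseline (Section 9.2). Guessing accuracy is not an estimate of bias, and none can be derived from the documents.

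All of that stands, and it limits the point. It does not close it. The non-disclosure instruction does not cover what staff read on forms. Besides the randomization form, Section 7.3 has research staff review all CORS forms weekly. Those forms are collected at TARA sessions and ask about change since the last class, so they may reveal the arm. That second route is an inference, and it lags, because classes may start up to four weeks after randomization (Section 6.2.2).

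**Conclusion.** The point holds as a gap in described concealment combined with an avoidable disclosure. It is not a finding that allocation is predictable. The protocol states the block structure of a single list that is open label to participants, and it leaves unassigned the task of obtaining and recording each assignment.

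If enrolling staff see past assignments and the blocks run in random order, they would guess the next arm correctly about 67–68% of the time, and about 5 of 92 assignments would be certain. If they do not see them, the rate is 50%. The documents neither establish nor rule out the first case. Who sees assignments therefore matters much more than whether block counts are printed. Separately, and without any assumption, the printed blocks give 92 places for a planned 100.

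**What to change.** 1. **Main remedy: roles.** State in Sections 6.2.2, 6.2.3 and 10.1 that the already planned unblinded RA obtains and records each assignment, and only after eligibility and baseline are complete. State that this RA does not screen or enrol, and that screening and enrolling RAs do not see assignments. Reconcile this with the wording in 6.2.3 that bars this RA from the data, since the randomization form is a source document; for example, limit the bar to outcome data.
2. **Secondary remedy: block details.** Remove sizes and counts from Sections 3, 4.3 and 9.2, keep them in a restricted randomization file, and leave only a statement that permuted blocks of varying size are used. In that file, correct the list so that it provides 100 places.

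The cost is minor rewording and a task reassignment among existing RAs, with no added staff or participants.
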